8.5. Medical Device Complaint Reporting Requirements

All medical device complaints, regardless of whether the medical device complaint is associated with an AE, will be recorded on the applicable pages within the CRF. This includes potential incidents or malfunctions associated with the use of a medical device

product. An incident or malfunction is an event that might have led to death or serious deterioration in health, or if it occurred again might lead to death or serious deterioration in health.

Pfizer is to be notified of all medical device complaints within 24 hours of the investigator's awareness of the event.

9. DATA ANALYSIS/STATISTICAL METHODS

Detailed methodology for summary and statistical analyses of the data collected in this study is outlined here and further detailed in a statistical analysis plan (SAP), which will be maintained by the sponsor. The SAP may modify what is outlined in the protocol where appropriate; however, any major modifications of the primary endpoint definitions or their analyses will also be reflected in a protocol amendment.

9.1. Analysis Sets

For safety evaluation, participants should have received at least one of the regimen components. For efficacy **CCI** evaluation, participants should have received at least one dose of all components administered on Cycle 1 Day 1. See Section **9.4** for definitions related to efficacy.

Participants who receive the designated investigational product of interest and have at least one post-dose drug concentration measurement will be included in the PK data analysis.

1. Safety analysis set.

The safety analysis set includes all enrolled participants who receive at least one dose of one of the components of the regimen.

2. Full analysis set.

The full analysis set includes all enrolled participants.

3. Per protocol analysis set.

The per protocol (PP) analysis set includes all enrolled participants who receive at least one dose of all regimen components administered on Cycle 1 Day 1 of study medication and who do not have major protocol deviations during the 28 days after the first vaccination.

4. Modified Intention-to-Treat analysis set.

CCI modified Intention-to-Treat (mITT), which is defined as all enrolled participants who received at least one dose of all regimen components administered on Cycle 1 Day 1.

CCI

a participant

must have at least 1 valid and determinate assay result related to the proposed analysis. Participants who have no valid and determinate assay result related to any proposed analysis will be excluded from the mITT analysis set.

CCI

5. PK analysis set.

The PK parameter analysis population is defined as all enrolled participants treated who have sufficient information to estimate at least 1 of the PK parameters of interest and who have no major protocol deviations influencing the PK assessment.

6. Immunogenicity analysis set.

The immunogenicity analysis set includes all enrolled participants who receive at least one dose of the VBIR-2 component that is the subject of the immunogenicity assessment (tremelimumab or sasanlimab).

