Protocol Activity	Screen (≤28 days)	Treatment Period								Maintenance	End of Treatment	Post Treatment					
		Cycle 1				Cycle 2						Every 4 months starting at Month 10	End of Treatment	Follow- Up (Months after EOT visit)			
Study Day		Day 1	Day 29	Day 57	Day 85	Day 113								M1	M2	M4	M6
Cycle Day						Day 1	Day 29	Day 57	Day 85					28-35 days			
Visit Window (days)			±2	±2	±2	±2	±2	±2	±2					±4	±4	±4	
Study Treatment																	
AdC68 ¹		X				X											
pDNA ²			X	X	X		X	X	X			X ²					
Tremelimumab ³		X	X	X	X	X	X	X	X			X ³					
Sasanlimab ⁴		X	X	X	X	X	X	X	X			X ⁴					
Pharmacokinetics Immunogenicity																	
PK for tremelimumab ⁵		X	X	X	X	X	X					X		X		X	X
ADA/NAb for tremelimumab ⁵		X	X		X		X					X		X		X	X
PK for Sasanlimab ⁶		X	X	X	X	X	X					X		X		X	X
ADA/NAb for Sasanlimab ⁶		X	X		X		X					X		X		X	X

Abbreviations: ADA = Anti-drug antibody; Adenovirus (AdC68); EOT = End of Treatment; pDNA = Plasmid deoxyribonucleic acid, PK = Pharmacokinetics

1. Adenovirus (AdC68) will be administered intramuscularly on Cycle 1 Day 1 and Cycle 2 Day 1. Tremelimumab and sasanlimab will be administered after the adenovirus for participants assigned to receive these components.
2. Plasmid DNA (pDNA) vaccinations will be administered intramuscularly using an electroporation device on Day 29, Day 57 and Day 85 of each cycle. During the Maintenance period, pDNA vaccinations will be administered every 2 months. All pDNA vaccinations should be administered prior to administering the tremelimumab and sasanlimab.
3. Tremelimumab will be administered subcutaneously in close proximity to the vaccine injected muscle and vaccine draining lymph nodes on Day 1, Day 29, Day 57 and Day 85 of each cycle. During the Maintenance period, tremelimumab will be administered every 2 months. Tremelimumab (both injections) will be administered after the adenovirus or pDNA and before the sasanlimab.

Protocol Activity	Screen (≤28 days)	Treatment Period							Maintenance	End of Treatment	Post Treatment			
		Cycle 1			Cycle 2						Follow- Up (Months after EOT visit)			
Study Day		Day 1	Day 29	Day 57	Day 85	Day 113					M1	M2	M4	M6
Cycle Day						Day 1	Day 29	Day 57	Day 85		28-35 days			
Visit Window (days)			±2	±2	±2	±2	±2	±2	±2			±4	±4	±4
Study Treatment														

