4. Sasanlimab will be administered subcutaneously in close proximity to the vaccine injected muscle and vaccine draining lymph nodes on Day 1, Day 29, Day 57 and Day 85 of each cycle. During the Maintenance period, sasanlimab will be administered each month. Sasanlimab will be administered after the adenovirus or pDNA and after the tremelimumab.
5. Blood samples for determination of tremelimumab drug concentrations and for detection of ADA/NAb against tremelimumab will be collected as outlined in the [schedule of activities](#). Samples to be collected on dosing days are to be obtained within 6 hours prior to tremelimumab dosing.
6. Blood samples for determination of sasanlimab drug concentrations and for detection of ADA/NAb against sasanlimab will be collected as outlined in the [schedule of activities](#). Samples to be collected on dosing days are to be obtained within 6 hours prior to sasanlimab dosing.

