9.6.3. Analysis of Immunogenicity Data

The percentage of participants with positive tremelimumab ADA and NAb will be summarized by each cohort. For participants with positive ADA or NAb, the magnitude (titer), time of onset, and duration of ADA or NAb response will also be described, if data permit.

The percentage of participants with positive sasanlimab ADA and NAb will be summarized by cohort. For participants with positive ADA or NAb, and if data permits, the magnitude (titer), time of onset, and duration of ADA or NAb response will be described.

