5.5. Other Analysis Sets

- *Per protocol analysis set.*

The per protocol (PP) analysis set includes all enrolled patients who receive at least one dose of all assigned regimen components administered Cycle 1 Day 1 of study medication and who do not have major protocol deviations during the 28 days after the first vaccination.

- *Modified Intention-to-Treat analysis set.*

CCI modified
Intention-to-Treat (mITT), which is defined as all enrolled patients who received at least one dose of all assigned regimen components administered. CCI

CCI a patient must have at least 1 valid and determinate assay result related to the proposed analysis. Patients who have no valid and determinate assay result related to any proposed analysis will be excluded from the mITT analysis set.

CCI

- *Immunogenicity analysis set.*

The immunogenicity analysis set includes all enrolled patients who receive at least one dose of the VBIR-2 component that is the subject of the immunogenicity assessment (tremelimumab or anti-PD-1 (PF-06801591)).

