8.2.1.2. Tremelimumab and PF-06801591 Immunogenicity

For patients receiving tremelimumab, the percentage of subjects with positive ADA and neutralizing antibodies will be summarized by dosing cohort. For patients with positive ADA, the magnitude (titer), time of onset, and duration of ADA response (in weeks and months) will also be described, if data permit.

For patients receiving PF-06801591, the percentage of subjects with positive ADA and neutralizing antibodies will be summarized by dosing cohort. For patients with positive ADA, the magnitude (titer), time of onset, and duration of ADA response (in weeks and months) will also be described, if data permit.

Time of onset will be calculated as (date of first positive ADA result - date of first dose of tremelimumab / PF-06801591 + 1). The duration of ADA response will be calculated as (Date of last positive ADA result - date of first positive ADA result + 1). Relevant descriptive statistics (namely mean, median, SD, min, max) maybe summarized for the magnitude (titer), time of onset, and duration of ADA response in weeks and months.

CCI

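### The SAP's ADA onset and incidence rules do not separate antibodies present before dosing from those that arise after it, and the immunogenicity set does not require a post-dose ADA result

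*Protocol*

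**What the plan says.** **Population.** Protocol 9.1 states: "The immunogenicity analysis set includes all enrolled participants who receive at least one dose of the VBIR-2 component" under assessment. SAP 5.5 has the same rule: "The immunogenicity analysis set includes all enrolled patients who receive at least one dose of the VBIR-2 component". Neither asks for an ADA sample or result. By contrast, Protocol 9.1 requires at least one post-dose concentration for the PK data analysis.

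**Incidence.** SAP 8.2.1.2: "For patients receiving tremelimumab, the percentage of subjects with positive ADA and neutralizing antibodies will be summarized by dosing cohort", with a parallel sentence for PF-06801591 (sasanlimab). Protocol 9.6.3: "The percentage of participants with positive tremelimumab ADA and NAb will be summarized by each cohort". Neither document defines baseline-positive, treatment-induced or treatment-boosted ADA.

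**Onset and duration.** SAP 8.2.1.2: "Time of onset will be calculated as (date of first positive ADA result - date of first dose of tremelimumab / PF-06801591 + 1"). Duration is the last positive date minus the first positive date, plus 1. Protocol 9.6.3 asks for onset and duration but gives no formula.

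**Sampling.** Both treatment and PK schedules in the protocol's Schedule of Activities include an ADA sample on Cycle 1 Day 1. The footnotes put it before dosing: "Samples to be collected on dosing days are to be obtained within 6 hours prior to tremelimumab dosing". The sasanlimab footnotes say the same.

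**Objective.** Protocol 2.1 and 2.2 list evaluation of the ADA response after subcutaneous administration as a secondary objective, with incidence and titers of ADA and neutralizing antibodies as the endpoint.

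**The concern.** An antibody detected before the first dose is not a response to that dose. The plan nevertheless lets it count towards incidence and gives it an onset date. It thus mixes pre-existing reactivity with what the objective asks about, and it pulls onset towards Day 1.

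Duration has two related weaknesses. A single positive sample is given a response of 1 day, although samples are weeks apart. A participant still positive at the last sample is treated as if the response ended that day.

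The set definition raises a separate question. A participant with no post-dose ADA result cannot show induced ADA, but a dose-only set keeps that participant in the base of the percentage.

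ADA status matters for reading the trough concentrations, which are also a secondary endpoint. In the monkey study in Protocol 1.4.1, lower exposure on Days 29 and 57 was attributed to ADA. Protocol 7.5 tests for neutralizing antibodies only in ADA-positive samples, so that summary inherits the same problem.

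**Working it through.** The documents state no ADA rate, so there is no figure to reproduce. The check applies the written rules and then varies the unknown counts.

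**Onset rule.** A pre-dose sample within 6 hours of dosing normally has the same calendar date as the first dose:

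- Pre-dose positive: onset = (date − same date) + 1 = 0 + 1 = Day 1.
- First positive 28 days after the first dose: onset = 28 + 1 = Day 29.

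Neither schedule includes a post-dose ADA sample on Day 1. In Part 2, as the extracted table reads, the first post-dose sample is Day 29. An onset of 1 from a scheduled sample is therefore a pre-dose positive.

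**Duration rule.** One positive sample: (date − same date) + 1 = 1 day.

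**Incidence.** Let N be the number dosed, u those with no evaluable post-dose ADA result, b the baseline-positives and t the treatment-induced cases.

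- Planned, as worded: (b + t) / N
- Treatment-induced: t / (N − u − b)

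N = 30 is the approximate Part 2 size (Protocol 9.3). The documents do not give u, b or t. Assumed: t = 6, u from 0 to 6, b from 0 to 3.

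| u | b | Planned | Treatment-induced |
|---|---|---|---|
| 0 | 0 | 6/30 = 20.0% | 6/30 = 20.0% |
| 3 | 0 | 6/30 = 20.0% | 6/27 = 22.2% |
| 6 | 0 | 6/30 = 20.0% | 6/24 = 25.0% |
| 0 | 2 | 8/30 = 26.7% | 6/28 = 21.4% |
| 0 | 3 | 9/30 = 30.0% | 6/27 = 22.2% |
| 3 | 3 | 9/30 = 30.0% | 6/24 = 25.0% |
| 6 | 3 | 9/30 = 30.0% | 6/21 = 28.6% |

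Missing post-dose results lower the planned figure relative to treatment-induced incidence, and baseline-positives raise it. When both occur the errors partly cancel, and the last row differs by only 1.4 points.

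**Onset summary (assumed cases).** Three induced cases first positive on Day 29 and three on Day 85 give a mean of (3×29 + 3×85)/6 = 342/6 = 57 days and a median of 57. Adding three baseline-positives at Day 1 gives a mean of (3 + 342)/9 = 38.3 and a median of 29.

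**Small cohorts.** SAP 2.1.2 plans 2 to 4 DLT-evaluable patients per escalation cohort. One baseline-positive among three patients, with no induced case, is reported as 1/3 = 33.3%, against a treatment-induced incidence of 0/2 = 0%.

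**The case against.** The denominator part is open to a strong reply. A reader might infer that the plan scores participants without a sample as ADA-negative. No passage says so: the documents define a set and promise a percentage, and are silent on missing results. Nor is it fair to suggest that many participants go unsampled. Every dosed participant is scheduled for the pre-dose Day 1 sample. Under Protocol 6.6, those who stop treatment stay in follow-up, and the Part 2 schedule reads as placing ADA samples at follow-up Months 1, 4 and 6, with Month 1 at 28 to 35 days. The gap is then confined to early death, full withdrawal of consent and loss to follow-up. This reply stands and limits that half of the point.

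Three further replies stand in part:

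- The onset and duration formulas appear only in a SAP written for the protocol dated 16 March 2018, which covers Part 1 in detail. The current protocol gives no formula, so Part 2 is affected only if the SAP rules are carried over.
- A Day 1 onset is recognisable, and the samples and titers needed to reclassify it will exist. The published summary would still be wrong until someone did so.
- The endpoint says incidence and does not promise treatment-induced incidence. But the objective it serves is response after administration, and a pre-dose positive does not measure that.

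**Conclusion.** The onset rule is a stated formula that gives an unsuitable answer whenever the pre-dose sample is positive: Day 1 onset and a place in the incidence count. The duration formula understates isolated or ongoing responses. The dose-only set is a smaller weakness, affecting only participants with no post-dose ADA result.

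A reader might conclude that the reported incidence will be wrong, or biased in a known direction. The documents do not support that. The effect requires at least one baseline-positive or one participant without a post-dose result; neither number is given, and the two errors oppose each other. Over the assumed range, the planned figure runs from 5.0 points too low (20.0% against 25.0%) to 7.8 points too high (30.0% against 22.2%), and is exact when neither occurs.

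The base of the percentage is read from the set definition together with the SAP's reference to patients receiving each antibody; no sentence names the denominator outright. The summaries are descriptive, with no test attached, and do not bear on DLT decisions, clinical benefit rate or sample size. The point is minor.

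**What to change.** Amend the SAP, and state that the rules apply to both parts:

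1. Compute treatment-induced ADA incidence among baseline-negative participants with at least one evaluable post-dose ADA result. Report how many dosed participants are excluded for lack of one.
2. Report baseline-positive and treatment-boosted participants separately, with the boosting criterion defined in advance from titer. Apply the same split to neutralizing antibodies.
3. Restrict onset and duration to post-dose positives in treatment-induced cases.
4. Flag duration as censored when the last available sample is positive, and show the number of positive samples beside each duration so that single positives can be seen.

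The samples are already scheduled and titers already planned, so no new data are needed. The cost is SAP wording, a little extra tabulation and slightly smaller denominators.

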9.2. Statistical Methods and Properties

9.2.1. Statistical Methods for Dose Escalation/De-Escalation

Many alternative designs have been proposed to the standard 3+3 design for Phase 1 dose escalation studies that improve its accuracy, efficiency and statistical validity. This study will utilize the mTPI design (Ji et al., 2010).¹⁴⁰

The mTPI design (Ji et al., 2010)¹⁴⁰ uses a Bayesian statistics framework and a beta/binomial hierarchical model to compute the posterior probability of 3 dosing intervals that reflect the relative difference between the toxicity rate of each dose level to the target rate ($pT = 0.275$). If the toxicity rate of the currently used dose level is far smaller than pT , the mTPI will recommend escalating the dose level; if it is close to target probability (pT), the mTPI will recommend continuing at the current dose; if it is far greater than pT , the mTPI will recommend de-escalating the dose level. These rules are conceptually similar to those used by the 3+3 design, except the decisions of a mTP design are based on posterior probabilities calculated under a coherent probability model.

Being a model-based design, mTPI automatically and appropriately tailors dose-escalation and de-escalation decisions for different studies with different toxicity parameters. More importantly, all the dose-escalation decisions for a given study can be pre-calculated under the mTPI design and presented in a two-way table (Table 3). It is currently envisaged that AdC68 6 x 10¹¹ VP + 5 mg pDNA + 150 mg tremelimumab + 300 mg sasanlimab will potentially be the highest dose level.

Thus, compared to other advanced model-based designs published in the literature, the mTPI design is logically less complicated and easier to implement.

Decision rules are based on calculating posterior probabilities of 3 dosing intervals corresponding to under, proper, and over dosing in terms of toxicity. Specifically, the underdosing interval is defined as $(0; pT - e_1)$, the over-dosing interval $(pT + e_2, 1)$, and the proper-dosing interval $(pT - e_1, pT + e_2)$, where e_1 and e_2 are small fractions. In this study, e_1 is selected as 0.05 and e_2 is selected as 0.05, therefore, the target interval for the DLT rate is $(0.225, 0.325)$. The 27.5% target, the symmetry of the Equivalence Interval, and its upper limit were chosen based on safety considerations. The prior distribution of DLT is set as a beta $(0.5, 0.5)$, and the threshold probability for early termination and dose exclusion is set to 0.95. Even though the upper limit of the mTPI is higher than 27.5%, doses with an incidence of DLT $>27.5\%$ (eg, 3 out of 9) cannot be declared as the MTD.

The 3 dosing intervals are associated with 3 different dose-escalation decisions. The underdosing interval corresponds to a dose-escalation I, overdosing corresponds to a dose de-escalation (D/U), and proper dosing corresponds to remaining at the current dose (S).

9.2.2. Statistical Method for Estimating the MTD

As previously described, the estimated MTD is the highest tested dose level with a DLT rate $\leq 32.5\%$ in at least 6 DLT-evaluable participants. It is assumed that higher doses result in higher toxicity rates. But, due to the relatively low number of participants that may be potentially allocated to any dose combination, this assumption may be incorrect, allowing for higher dose levels to be tested.

Clinical judgment will be exercised in taking forward doses to the expansion cohort(s), in case no clear choice exists between more than 1 competing MTD. This decision will be based upon the combination of data related to safety, anti-tumor activity, and clinical judgment of the investigators and the sponsor.

9.3. Sample Size Determination

It is anticipated that each of the cohorts will aim to enroll 2-4 participants, with the exception of the cohort with the anticipated MTD dose that will aim to enroll up to 12 participants. Due to the dynamic nature of the Bayesian allocation procedure, the sample size of the mTPI approach cannot be determined in advance. It is estimated approximately 36 DLT evaluable participants may be enrolled in the dose escalation stage in order to have a reliable and accurate estimate of the MTD. The actual sample size for the dose escalation may be smaller, depending on the underlying dose toxicity profile.

At least 6 and up to 12 participants should be enrolled at a dose level that is predicted to be the MTD as per the mTPI method. Dose cohorts with an acceptable safety profile may be expanded up to N=12 to further assess safety, CCI [REDACTED] pharmacokinetics, CCI [REDACTED] [REDACTED] Decisions to enroll additional participants at dose levels already cleared for safety will be based on clinical judgment of the investigators and the sponsor considering all evaluable safety, CCI [REDACTED] data.

The expansion phase of the study (Part 2) will consist of 1 cohort of participants with metastatic or locally-advanced NSCLC. Approximately 30 participants will be enrolled for

the dose expansion. A Bayesian approach will be used to estimate the objective response rate (ORR) and clinical benefit rate (CBR) in the study indications. As an example of this approach related to ORR, assuming a non informative prior (ie, Jeffrey's prior), if 14 out of 30 participants (46.7%) achieve a CR or PR, this would translate into a posterior probability (Beta Binomial) of 77% that the true ORR/clinical benefit rate is not inferior to 20%. (See Definitions of ORR and CBR in Section 9.4).

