2.2. Part 2: Dose Expansion Objectives and Endpoints

Primary Objective(s): Part 2	Primary Endpoint(s): Part 2

 • To document preliminary evidence of anti-tumor activity using the Clinical Benefit rate (CBR) in participants with NSCLC. • To assess safety and tolerability of VBIR-2 in participants with NSCLC. 	
 • CBR (proportion of participants who achieve Complete Response, Partial Response or Stable Disease for > 6 months) using the Response Evaluation Criteria in Solid Tumor (RECIST) version 1.1 (Appendix 3). • Adverse Events as characterized by type, frequency, severity, timing, seriousness, and relationship to study therapy. • Laboratory abnormalities as characterized by type, frequency, severity, and timing.
Secondary Objective(s): 
 • To document preliminary evidence of anti-tumor activity in participants with NSCLC. • To evaluate the PK of tremelimumab and of sasanlimab after SC administration. • To evaluate the anti-drug antibody (ADA) response of tremelimumab and sasanlimab after SC administration with the other components. 	Secondary Endpoint(s): 
 • Objective Response Rate (ORR), Duration of Response (DOR) and Progression-Free Survival (PFS) using RECIST version 1.1 (Appendix 3). • Overall survival (OS). • Tremelimumab and sasanlimab trough concentrations after multiple dosing (C_{trough}) at various time points. • Incidence and titers of ADA and neutralizing antibodies against tremelimumab and against sasanlimab.

CCI

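### The Part 2 worked example in Protocol Section 9.3 does not compute: 14/30 with a Jeffreys prior gives a 99.95% posterior probability that the rate exceeds 20%, not 77%

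*Protocol*

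**What the plan says.** Protocol Section 9.3 plans one NSCLC expansion cohort ("Approximately 30 participants will be enrolled for" Part 2) and proposes Bayesian estimation of ORR and CBR. It then gives one worked example, all within one sentence:

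- **Endpoint and prior:** "As an example of this approach related to ORR, assuming a non informative prior (ie, Jeffrey's prior").
- **Data:** "if 14 out of 30 participants (46.7%) achieve a CR or PR".
- **Result:** "this would translate into a posterior probability (Beta Binomial) of 77% that the true ORR/clinical benefit rate is not inferior to 20" percent.

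The sentence refers the reader to Section 9.4 for the definitions of ORR and CBR. Section 2.2 makes CBR a primary endpoint of Part 2 and defines it as "CBR (proportion of participants who achieve Complete Response, Partial Response or Stable Disease for > 6 months"). ORR is a secondary endpoint there.

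No other section gives a different prior, count or reference rate for this calculation. The SAP is written to the March 2018 protocol and describes the former three-cohort Part 2 (SAP Sections 2.1 and 4.1). It has no counterpart to this example.

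**The concern.** The sentence supplies every input needed to check it, and the answer looks wrong on sight. An observed rate of 46.7% in 30 participants lies far above 20%, so a posterior probability as low as 77% of exceeding 20% is not credible under a non-informative prior.

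Section 9.3 is where an investigator, ethics committee or later statistician looks for what about 30 participants can establish, and this is its only numerical answer for ORR or CBR. As printed, it says that almost half the cohort responding leaves only moderate confidence of clearing 20%. If instead the 20% is the slip, the intended benchmark was about twice the printed one, which is a different message about what activity would be of interest. Anyone carrying the example into an updated SAP, or using it to validate code, would start from a figure that cannot be reproduced.

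There is a smaller labelling fault. The example is introduced as concerning ORR and counts only CR and PR, but its conclusion is stated for ORR and CBR alike. CBR also counts stable disease lasting more than 6 months, so a count of CR and PR is not a CBR count.

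**Working it through.** **Inputs, all from Protocol Section 9.3**

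- n = 30 and x = 14, so x/n = 14/30 = 46.7%. The printed count and percentage agree.
- Prior: Jeffreys. The section gives no parameters. The standard form for a binomial rate is Beta(0.5, 0.5), which is also the prior named for the DLT rate in Section 9.2.1.
- Reference rate: 20%, with no separate non-inferiority margin.

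**Step 1: the plan's own figure.** The posterior is Beta(x + 0.5, n − x + 0.5) = Beta(14.5, 16.5). The quantity described is P(p > 0.20) = 1 − F(0.20), where F is the Beta(14.5, 16.5) distribution function. This equals 0.99954, or 99.95%. The stated 77% is not reproduced; the gap is 99.95 − 77 = about 23 percentage points.

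A hand check agrees. The posterior mean is 14.5/31 = 0.468 and the posterior SD is √[14.5 × 16.5 / (31² × 32)] = 0.088. The 20% reference therefore lies (0.468 − 0.20)/0.088 ≈ 3 SDs below the mean.

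**Step 2: is it the prior?** At the 20% reference with 14/30:

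| Prior | P(p > 20%) |
|---|---|
| Jeffreys | 99.95% |
| Uniform, Beta(1, 1) | 99.96% |
| Haldane (limit) | 99.94% |

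No.

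**Step 3: is it the approximate n?** Keep 14 responders and the Jeffreys prior, and take n from 26 to 36 as an assumed reading of approximately 30. The probability runs from 99.99% (n = 26) to 99.6% (n = 36). It would take n of about 59 to bring it down to 77% (0.768).

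**Step 4: is it the count?** With n = 30, Jeffreys and 20%, 7 responders give 68.9% and 8 give 82.2%. No whole number out of 30 gives 77%. Over n = 26 to 36, only 8/32 rounds to it (76.7%), and that contradicts the printed 14, 30 and 46.7% all at once.

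**Step 5: is it the reference rate?** With 14/30 and Jeffreys:

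| Reference | P(p > reference) |
|---|---|
| 20% | 99.95% |
| 25% | 99.5% |
| 30% | 97.4% |
| 35% | 90.8% |
| 40% | 77.3% |
| 45% | 57.5% |

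Only references between 39.95% and 40.24% round to 77%. A 40% reference is therefore the one simple single-entry change to the inputs that restores the printed probability.

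**Step 6: is it a different quantity?** A non-inferiority margin would lower the effective threshold below 20% and push the probability higher still. Treating 20% as a margin below the observed rate gives a threshold of 46.7% − 20% = 26.7%, and P(p > 26.7%) = 0.991. The posterior predictive probability of at least 6 responders (20%) in a further 30 participants is also 0.991. None of these gives 77%.

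**The case against.** The strongest reply is about weight. The sentence is offered as an example. The rationale for Amendment 2 says the Part 2 sample size was not set quantitatively, Section 9.4 plans descriptive summaries of ORR and CBR, and no go/no-go rule uses the 77%. Correcting it changes no endpoint, analysis or participant. That all stands, and it caps the importance of the point.

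A second reply is that reporting 99.95% presumes the probability is the faulty entry, when the near-exact match at 40% suggests the reference rate may be. That is fair as a caution about the remedy. The 99.95% is what the printed inputs imply. It is not a claim about what the sponsor meant, and the 40% reading is an inference that no section confirms.

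Third, changing a single digit (20 to 40) reconciles the sentence, so a slip in the copy at hand cannot be fully excluded. Nothing in the paragraph points to one, and 14/30 and 46.7% agree with each other. A look at the source page would settle it.

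Fourth, the label does not alter the arithmetic, because the same posterior applies to any endpoint with 14 successes in 30. This is correct, so the labelling point is secondary. It still matters that the example's definition of success is CR or PR, which is not the definition of CBR.

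**Conclusion.** The concern holds. On its own inputs the example should read 99.95%, not 77%. The discrepancy survives a change of prior, any responder count out of 30, sample sizes from 26 to 36 with 14 responders, and the margin and predictive readings of the sentence. If 14/30 and 77% are both kept, the reference must be about 40%. The documents do not say whether the probability, the reference or the count is wrong.

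The conclusion assumes the standard Beta(0.5, 0.5) form of the Jeffreys prior and reads not inferior to 20% as a true rate above 20%. The result is not sensitive to either assumption. The consequence is limited to one illustrative sentence, but that sentence is the only quantitative property stated for Part 2 on ORR or CBR, so it should be corrected.

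**What to change.** The sponsor should go back to the source calculation, establish which entry is wrong, and rewrite the sentence in Protocol Section 9.3 so that count, reference rate and probability agree:

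- If 14/30 and 20% were intended, replace 77% with >99.9%.
- If 40% was the intended reference, keep 77% and change 20% to 40%.
- If the count is wrong, restate it with its matching percentage and recomputed posterior probability.

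In each case, state the prior as Beta(0.5, 0.5) and label the result as ORR only, because success is defined as CR or PR.

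The cost is one corrected sentence. The sample size, endpoints and stated decision rules are unchanged. The supplied SAP has no corresponding text to amend; a future SAP covering the single-cohort Part 2 should carry the corrected version.
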